6. EFFICACY ANALYSIS

All efficacy analyses will be summarized for each study part. Efficacy data will also be analyzed by treatment group in Part 2. Hypothesis testing will be performed for part 2 between two treatment groups.

Unless otherwise specified, baseline for all efficacy analyses is defined as the last non-missing measurement recorded prior to taking the first dose of study drug.

All CIs will be presented as 2-sided 90% and/or 95% CIs. All statistical tests will be 2-sided hypothesis tests performed at the 10% level of significance.

The primary efficacy analyses will be performed for full analysis set (FAS). The supportive efficacy analyses will be performed for Intent-to-Treat (ITT) set.

6.1 Analysis of Primary Efficacy Endpoint

Not Applicable.

6.2 Analysis of Secondary Efficacy Endpoints

6.2.1 Time-to-event endpoints

The following time-to-event endpoints are defined as:

- Hospital length of stay: initiation of study drug (Day 1, for Part 1) or randomization date (for Part 2) to hospital discharge. For subjects with death of any cause or withdrawal of study participation, hospital length of stay will be imputed with the longest hospital length of stay observed in the study.
- Overall survival: initiation of study drug (Day 1, for Part 1) or randomization date (for Part 2) to death of any cause; censored at the last day known to be alive.
- Total duration of mechanical ventilation defined as days on mechanical ventilation during the study participation, calculated as follows:
 - For subjects with death of any cause (or withdrawal of study participation), total duration of mechanical ventilation will be imputed with the longest duration observed in the study.
 - For any subject who is on mechanical ventilation at the initiation of study drug (Day 1, for Part 1) or at the randomization date (for Part 2), total duration of mechanical ventilation is calculated from Day 1 or randomization date.
 - For any subject who is not on mechanical ventilation at the initiation of study drug (Day 1, for Part 1) or at the randomization date (for Part 2), patient will be excluded.
- Total duration of oxygen therapy defined as days on mechanical ventilation or supplemental oxygen during the study participation, calculated as follows:

- For subjects with death of any cause (or withdrawal of study participation), total duration of oxygen therapy will be imputed with the longest duration observed in the study.
- For any subject who is on mechanical ventilation or supplemental oxygen at the initiation of study drug (Day 1, for Part 1) or at the randomization date (for Part 2), total duration of oxygen therapy is calculated from Day 1 or randomization date.
- For any subject who is not on mechanical ventilation or supplemental oxygen at the initiation of study drug (Day 1, for Part 1) or at the randomization date (for Part 2), patient will be excluded.

The p-values will be from a 2-sided unstratified Log-rank test and stratified Log-rank test by the randomization stratification factors [need of mechanical ventilation (yes vs no) and age (younger than 65 years vs at least 65 years)] at 0.1 significant level for evaluation of treatment difference. These time-to-event endpoints will be summarized via Kaplan-Meier (KM) methodology using the 25th, 50th (median), and 75th percentiles and pre-specified timepoints, each with associated 2-sided 90% confidence intervals. Point estimate of hazard ratio will be obtained from a Cox regression model with treatment and the randomization stratification factors as fixed factors and the 90% CI will be obtained using Wald method.

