## Part 2 (Randomized Double-Blind Period):

Part 2 of the study will be initiated only upon recommendation from the DMC. Required criteria for initiation of Part 2 will include (1) no fatal/life-threatening SAEs thought possibly related to APL-9 by the DMC, and (2) no more than 1 subject requiring premature treatment discontinuation by the investigator due to AEs or abnormal laboratory tests. All subjects will receive SOC independent of their randomization. Approximately 60 subjects will be randomly

assigned in a 1:1 ratio to blinded treatment with either APL-9 or saline vehicle. Subjects will receive treatment with APL-9 or vehicle from Day 1 through Day 7, discontinuation of respiratory support (supplemental oxygen or mechanical ventilation), or hospital discharge, whichever occurs latest.

Subjects may receive treatment beyond Day 7 if the DMC approves an extended treatment duration following the review of data from Part 1 or during the conduct of Part 2. The DMC may approve any extended treatment duration up to and including Day 21; extended treatment will be allowed only in subjects who still require respiratory support (oxygen supplementation or mechanical ventilation) at Day 7 with an improved PaO2/FiO2 ratio of at least 20 mm Hg from baseline if arterial blood gas (ABG) test results are available for comparison. If ABG test results are not available, an improvement in FiO2 of at least 4% in nonventilated patients (eg, those on nasal cannula) and 10% in mechanically ventilated patients is needed. FiO2 should be weaned following the site's protocol to keep oxygen saturation at 89% or above. Treatment beyond Day 7 and through any DMC-approved extension will be at the discretion of the investigator. Treatment beyond Day 7 and up to and including any DMC-approved extension will be at the discretion of the investigator.

Follow-up safety assessments for each subject will be collected 30 days following the last dose of study treatment (up to and including Study Day 51 with a +7-day window). Safety assessments may be performed any time during the 30-day follow-up period at the investigator's discretion but are required 30 days after the last dose of study drug (up to and including Study Day 51 with a +7-day window). These assessments will be conducted via inpatient assessment (for subjects still hospitalized) or by telephone call (for subjects discharged).

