- i The concomitant procedures include recording the day that the subject was admitted to the ICU (or ICU-type environment), use of ventilatory support, use of oxygen therapy, date of ICU discharge, date of hospital discharge, and survival. The time and date of any changes to concomitant medications and procedures are to be recorded at the days indicated in the schedule of assessments. In case of early hospital discharge, the data is collected via phone interviews.

#### APL-9 APL9-COV-201 Protocol Amendment 3

- j Infusion-related reactions that occur during the administration of the 50-mL loading dose should be treated as follows: For mild infusion-related reactions: The 50-mL bag infusion time should be increased from 10 min to 20-40 min and the reaction should be monitored. Treatment with diphenhydramine may be required. The infusion time of the 250-mL bag should not be increased. For severe or persistent mild infusion-related reactions (instances in which the subject's symptoms do not respond to the increased infusion time), treatment should be discontinued, and the institution's emergency hypersensitivity protocol should be employed. Refer to the procedure for handling infusion-related reactions in Section 9.1.1.
- k Confirmation of SARS-CoV-2 infection for screening may be completed more than 7 days before baseline.
-  Vaccination history should be attempted to be collected as a component of medical history.
- m A PK/PD assessment will be done on the last day of treatment. If EOT and discharge day visit are on different days, a PK/PD sample will be collected on the discharge day as an unscheduled visit.
- n If EOT and day of discharge visit are on different days, perform EOT assessments on the last day of treatment and repeat on the day of discharge as an unscheduled visit. Perform/record vital signs, ECG, concomitant medications/procedures, infusion site reactions, and AEs daily up to and including day of discharge. After EOT, record as unscheduled visits.

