### **10.2.** Subject Discontinuation/Withdrawal From the Study

- A subject may withdraw from the study at any time at his/her own request (or at the request of his/her legal representative) or at the discretion of the investigator for safety, behavioral, compliance, or administrative reasons.
- At the time of discontinuing from the study, if possible, an end-of-treatment visit should be conducted, as shown in the SoA. See the SoA for data to be collected at the time of study discontinuation and follow-up and for any further evaluations to be completed. The subject will be permanently discontinued both from the study intervention and from the study at that time.
- If the subject withdraws consent for disclosure of future information, the sponsor may retain and continue to use any data collected before such a withdrawal of consent.
- Subjects who withdraw from the study may request destruction of any samples taken and not tested, and the investigator must document this in the site study records.

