## **10.3.** Lost to Follow-up

A subject will be considered lost to follow-up for failure to complete the safety follow-up assessment 30 days after the last dose of study drug (up to Study Day 51 with a +7-day window).

The following actions must be taken if a subject fails to complete the required safety follow-up assessment 30 days after the last dose of study drug (up to Study Day 51 with a +7-day window):

- The site must attempt to contact the subject and reschedule the missed visit as soon as possible, counsel the subject on the importance of final study assessments, and ascertain whether the subject wishes to and/or should continue in the study.
- Before a subject is deemed lost to follow-up, the investigator or designee must make every effort to regain contact with the subject (where possible, 3 telephone calls and, if necessary, a certified letter to the subject's last known mailing address or local equivalent methods). These contact attempts should be documented in the subject's medical record.
- Subjects who continue to be unreachable will be considered to have withdrawn from the study.

Closure of specific sites or of the study as a whole are described in Section 13.1.7.

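### SAP 6.2.1 replaces a known hospital stay with the longest in the study when a discharged subject later withdraws or cannot be reached

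*SAP*

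**What the plan says.** SAP 6.2.1 runs the stay from randomization (Part 2) or Day 1 (Part 1) to hospital discharge. The imputation sentence follows: "For subjects with death of any cause or withdrawal of study participation, hospital length of stay will be imputed with the longest" stay observed in the study. It sets no condition on when the death or withdrawal occurred. In the same section, overall survival is "censored at the last day known to be alive"; the stay has no censoring rule. Both endpoints are then "summarized via Kaplan-Meier (KM) methodology using the 25th, 50th (median), and 75th percentiles", tested with unstratified and stratified log-rank at two-sided 10%, and given a Cox hazard ratio.

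The protocol says who counts as withdrawn and when that can happen:

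- Section 10.2: "A subject may withdraw from the study at any time at his/her own request".
- Section 10.3, on subjects who miss the 30-day safety assessment: "Subjects who continue to be unreachable will be considered to have withdrawn from the study".
- Section 7.1, on how that assessment is done: "via inpatient assessment (for subjects still hospitalized) or by telephone call (for subjects discharged").
- Table 1, footnote i, lists the recorded items, among them "date of ICU discharge, date of hospital discharge, and survival". Footnote n adds that when treatment ends before discharge, the site must carry out the end-of-treatment assessments and "repeat on the day of discharge as an unscheduled visit".

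**The concern.** Read together, these sections let a subject become withdrawn after the stay has ended and its length is on file. Whether someone answers the telephone weeks after going home says nothing about how long they were in hospital. Overwriting that stay puts a wrong value where a right one exists, and always in the direction of a longer stay.

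Three things are at stake for this endpoint:

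- the reported percentiles of stay in each arm;
- the power of the comparison;
- if more stays are overwritten in one arm than in the other, the type I error and the hazard ratio.

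Two gaps sit beside it. The rule does not separate death after discharge from death in hospital. It also does not say whether an imputed stay enters Kaplan-Meier and Cox as an event or as censored, although Protocol 12.3.2 expects time-to-event estimates that allow for censoring.

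**Working it through.** **Text.** The outcome is complete at discharge (SAP 6.2.1). The trigger can arise later (Protocol 10.2, 10.3 and 7.1). The discharge date is collected (Table 1, footnotes i and n). Nothing in either document exempts discharged subjects. Where the SAP authors wanted a timing condition they wrote one: SAP 6.3.2 and 6.3.3 impute the duration of new oxygen or ventilator use only for death or withdrawal that follows the restart. Section 6.2.1 has no such limit.

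**Plan's own figures.** The plan gives none for this endpoint. Its only sample-size figures are the chances of seeing an SAE in 30 subjects. They reproduce as 1 - (1 - p)^30 = 26.0%, 70.6%, 88.7% and 95.8% at p = 1%, 4%, 7% and 10%. They supply the arm size of 30 used below and nothing else.

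**One overwritten stay.** The arm mean rises by (longest - actual)/30. For an 8-day stay:

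- longest 30 days: (30 - 8)/30 = 0.73 days
- longest 40 days: (40 - 8)/30 = 1.07 days
- longest 51 days: (51 - 8)/30 = 1.43 days

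The SAP plans no mean stay, so this only gives a sense of scale.

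**Kaplan-Meier 75th percentile, n = 30.** The proportion still in hospital must fall to 25% or less. After 22 discharges it is 8/30 = 0.267; after 23 it is 7/30 = 0.233. So 23 observed discharges are needed. With 6 deaths (assumed) and all others discharged there are 24. Two overwritten stays leave 30 - 6 - 2 = 22. The percentile then reads as the longest stay if imputed values are events, and as not reached if they are censored.

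**Simulation.** Assumptions: 2,000 trials per scenario; 30 per arm; 20% in-hospital mortality; stays exponential or lognormal (log-SD 0.8), with medians 12 vs 12 days (null) or 12 vs 7 (power); subjects still in hospital at Day 51 or Day 28 censored there; strata of 30% ventilated and 40% aged 65 or over, with no prognostic effect. Imputed values were coded both ways. Tests were at two-sided 10%. Simulation standard error near 10% is √(0.1 × 0.9/2000) = 0.7 points.

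Rejection (%) with no true effect, SAP rule as written:

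| Overwritten stays, or loss after discharge | Log-rank, unstratified and stratified | Cox (Wald) |
|---|---|---|
| 10% vs 10% | 9.5-11.2 | 6.3-11.2 |
| 0 vs 1 stay | 10.5-11.9 | 7.8-11.2 |
| 0 vs 2 stays | 11.5-15.2 | 8.3-15.1 |
| 0 vs 3 stays | 14.4-21.0 | 11.0-20.5 |
| 5% vs 10% | 10.4-13.0 | not tabulated |
| 0% vs 10% | 11.9-17.0 | 9.1-16.6 |
| 5% vs 20% | 14.0-23.3 | 9.4-22.8 |

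Keeping the recorded discharge date in the same runs gives 9.0-11.9 (log-rank) and 6.7-12.4 (Cox). Cox is conservative when imputed values are tied events.

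- *Equal 10% loss:* control mean up 2.5-2.7 days (Day 51 limit) or 1.0-1.2 days (Day 28); Kaplan-Meier median up 2-4 days, for example 17 to 20; power down about 3-9 points. In the exponential, Day 51, events case, power goes from 29.5% to 23.2% (log-rank), 29.1% to 23.6% (stratified) and 23.8% to 16.0% (Cox).
- *One overwritten stay in each arm:* median up 1-2 days; power down about 1-5 points.
- *0 vs 3 stays, no true effect:* median hazard ratio for discharge 0.84-0.88 with events and 0.78-0.79 with censoring, so the unstated coding changes the estimate.

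**Sensitivity to mortality.** A separate run with no deaths (lognormal stays, median 10 days, log-SD 0.7, capped at 51; unstratified log-rank, imputed values as events; 3,000 trials) gives about 30% rejection at 10% vs 0% loss, and still near 10% with equal loss. Deaths take the same imputed value in both arms and dilute the contrast, so the table is the more cautious set.

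**The case against.** The strongest reply is that imputation normally fills a missing value, and a recorded discharge date is not missing. A sensible programmer might apply the rule only where discharge was not observed, and the authors may have meant that. This is plausible. But the sentence is keyed to withdrawal status, the contrast with SAP 6.3.2 and 6.3.3 points the other way, and a program that follows the text would overwrite the stays.

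Several narrower objections stand:

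- Mean stay is not a planned summary.
- The 75th-percentile example works only with 6 or 7 deaths. With 5 or fewer, at least 23 discharges remain; with 8 or more, 23 are never reached.
- Blinding, and the calls and certified letter that Protocol 10.3 asks for, give no reason to expect a large imbalance in loss. Inflation is a possibility, not a prediction.
- No efficacy endpoint is powered, so the loss of power carries limited weight.
- SAP 1 says the SAP supersedes the protocol's analysis plan, so Protocol 12.3.2 does not settle the coding. The SAP's own silence remains, and SAP 14.1 declares no change from the protocol.

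The ventilation and oxygen rules in 6.2.1 share the unconditioned wording. The difference is that support used after discharge is learned by telephone and is unknown in an unreachable subject, whereas the stay is already complete.

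**Conclusion.** The concern holds. As written, SAP 6.2.1 replaces a completed, recorded stay with the study maximum for any discharged subject who later withdraws or stays unreachable, and it leaves the coding of imputed stays unspecified.

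With equal loss the harm is longer reported stays and some lost power, with no inflation of type I error. A single overwritten stay in one arm has little or no effect on the test. Two or three in one arm against none raise the false-positive rate visibly. The loss rates, mortality and stay distributions are all assumed. The reading of the text does not depend on them. The effect is confined to a secondary endpoint; the primary safety endpoint is untouched. It is worth correcting because the rule is wrong on its face and an arm of about 30 is sensitive to a few subjects.

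**What to change.** In SAP 6.2.1:

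1. Use the recorded discharge date for every subject who withdraws or is lost to follow-up after discharge. Apply the longest-stay value for withdrawal only when it precedes discharge.
2. State whether death after discharge takes the worst value. Either choice can be defended and is the sponsor's to make.
3. State whether imputed stays enter Kaplan-Meier and Cox as events or as censored, and at what time.

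Worst-value scoring of deaths, and the ventilation and oxygen rules, can stay as they are. The cost is SAP wording and programming. No new data are needed, because the discharge date is already collected. The change should be made before unblinding.

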#### Secondary:

- Hospital length of stay (measured in days)
- Any-cause mortality (measured from beginning of treatment until the safety follow-up assessment 30 days after last study treatment [up to and including Study Day 51 with a +7-day window])
- SOFA score
- Total duration of mechanical ventilation (measured in days)

- Total duration of oxygen therapy (by continuously worn mask or nasal cannula, measured in days)
- APL-9 PK parameters
- Observed values and changes from baseline in markers of complement activation (C3, C3a, C4, C4a, Bb, C5a, terminal complement complex, and alternative complement pathway hemolytic activity), coagulopathy (reticulocyte count, presence of schistocytes, lactate dehydrogenase, D-dimer, ferritin, haptoglobin, fibrinogen), and inflammatory cytokines (C-reactive protein [CRP], tumor necrosis factor α [TNFα], IL-1β, and IL-6)

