## 6.2.2. Secondary Objective Endpoints

- Hospital length of stay (measured in days)
- Any-cause mortality (measured from beginning of treatment until the safety follow-up assessment 30 days after last study treatment [up to and including Study Day 51 with a +7-day window])
- SOFA score
- Total duration of mechanical intervention (measured in days)
- Total duration of oxygen therapy (by continuously worn mask or nasal cannula, measured in days)
- APL-9 PK parameters
- Observed values and changes from baseline in markers of complement activation (C3, C3a, C4, C4a, Bb, C5a, TCC, and alternative complement pathway hemolytic activity [AH50]), coagulopathy (reticulocyte count, schistocytes, lactate dehydrogenase, D-dimer, ferritin, haptoglobin, and fibrinogen), and inflammatory cytokines (C-reactive protein [CRP], tumor necrosis factor α [TNFα], IL-1β, and IL-6).

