### 12.3.2. Analysis of Secondary Efficacy Endpoints

Continuous variables will be summarized using descriptive statistics (eg, median and mean); for categorical variables, the frequency and percentage in each category will be displayed. Time-to-event data (such as time to hospital discharge and time to mechanical ventilation discontinuation) will be summarized using Kaplan-Meier estimates accounting for censored observations (and analyzed using the Cox proportional hazard model if appropriate).

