2.2.3 Exploratory Objective Endpoints

- Presence of active SARS-CoV-2 infection at the end-of-treatment visit. Presence of SARS-CoV-2 viral RNA or viral antigen may be detected in respiratory specimens (collected using nasopharyngeal or oropharyngeal swabs) with a qualitative nucleic acid amplification test (such as reverse transcriptase polymerase chain reaction [RT-PCR]), viral antigen test, or other diagnostic method that is authorized, cleared, or approved by the US Food and Drug Administration (or equivalent local authority) for SARS-CoV-2 viral detection. Serology-based antibody tests do not detect the presence of virus and therefore are not considered diagnostic and cannot be used for study eligibility screening or for subsequent SARS-CoV-2 assessments.
- Incidence, duration, and extent of new oxygen therapy use (re-initiation 24 hours or more after cessation of prior oxygen therapy)
- Incidence, duration, and extent of new mechanical ventilation use (re-initiation 24 hours or more after cessation of prior mechanical ventilation)
- CCI

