14. CHANGES TO ANALYSES

14.1 Changes to Analyses Specified in the protocol

Not applicable

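### SAP 6.2.1 limits ventilation duration to subjects ventilated at baseline without declaring the change, and a first ventilation in a subject who entered on oxygen is in neither readable ventilation endpoint

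*SAP*

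**What the plan says.** The protocol synopsis lists "Total duration of mechanical ventilation (measured in days") as a secondary endpoint. Protocol 6.2.2 has the same item as "Total duration of mechanical intervention (measured in days"). Neither sets a baseline condition, and Protocol 12.3.3 names no subset for the time-to-event analysis. SAP 2.2.2 repeats the endpoint unrestricted, and SAP 4.4 assigns efficacy analyses to the full analysis set.

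SAP 6.2.1 opens in the same way: "Total duration of mechanical ventilation defined as days on mechanical ventilation during the study participation". It then gives three rules. After death or withdrawal, "total duration of mechanical ventilation will be imputed with the longest duration observed in the study". For subjects ventilated at the start, duration runs from Day 1 (Part 1) or randomization (Part 2). For a subject without "ventilation at the initiation of study drug (Day 1, for Part 1) or at the randomization date (for Part 2), patient will be excluded". The order in which the first and third rules apply is not stated.

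The body of SAP 14.1, under "Changes to Analyses Specified in the protocol", says that the section does not apply.

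The other readable ventilation endpoint is exploratory (Protocol 6.2.3; SAP 2.2.3 and 6.3.3): "Incidence, duration, and extent of new mechanical ventilation use (re-initiation 24 hours or more after cessation of prior mechanical ventilation".

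**The concern.** Time on mechanical ventilation is a secondary objective in both documents. Subjects on supplemental oxygen alone are eligible (Protocol 8.1), and subjects not needing ventilation form a randomization stratum (SAP 3.3). Going onto a ventilator for the first time is the ventilation outcome those subjects can have, and it is in neither ventilation endpoint.

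Two things are at stake. The analysis of this objective cannot show an effect, in either direction, on progression to ventilation in the non-ventilated stratum. And because the restriction is absent from the endpoint lists and from SAP 14.1, a reader may take a result from the ventilated-at-baseline subset as covering everyone randomized.

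**Working it through.** **1. The plan's own figures.** None is given for ventilation. The only sizing figures are the chances of at least one SAE among 30 subjects. They reproduce as 1 - (1 - p)^30 = 26.0%, 70.6%, 88.7% and 95.8% at p = 1%, 4%, 7% and 10%, but have no bearing here.

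**2. Follow one subject through the outputs.** The subject enters on nasal oxygen, is ventilated later without coming off oxygen, and survives to complete the study.

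- Ventilation duration (SAP 6.2.1): excluded, because not ventilated at baseline.
- New ventilation use (SAP 6.3.3): not counted, because no earlier ventilation had stopped.
- New oxygen therapy use (SAP 6.3.2): not counted, because there was no 24-hour gap off oxygen.
- Total oxygen-therapy duration (SAP 6.2.1): the days count, but a ventilator day and a nasal-cannula day count alike.
- SOFA and adverse-event tables: indirect at most.
- Concomitant procedures (SAP 5.5): counted, together with subjects whose ventilation was ongoing at first dose.
- Listings (SAP 5, 12.1 and 12.6.3): visible by subject and arm, with dates as recorded.

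One exploratory endpoint is redacted and cannot be judged.

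**3. How many subjects.** Part 2 has about 60 subjects (SAP 3.3). The share q ventilated at baseline and the share r of the others ventilated later are assumptions. Analysed = 60q; excluded = 60(1 - q); first episodes in neither endpoint = 60(1 - q)r.

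| q | analysed | excluded | first episodes, r = 10% | first episodes, r = 30% |
|---|---|---|---|---|
| 10% | 6 | 54 | 5.4 | 16.2 |
| 20% | 12 | 48 | 4.8 | 14.4 |
| 30% | 18 | 42 | 4.2 | 12.6 |
| 50% | 30 | 30 | 3.0 | 9.0 |

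As a share of all subjects ever ventilated, this runs from 3.0/(30 + 3.0) = 9% to 16.2/(6 + 16.2) = 73%.

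**4. What the subset cannot show.** Suppose treatment only lowered later ventilation among non-ventilated subjects from 30% to 15%, at 10 days per episode (all assumed). The mean difference in ventilation days over all subjects is (1 - q) x 0.15 x 10: 1.35 days at q = 10% and 0.75 days at q = 50%. In the SAP 6.2.1 subset it is zero.

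**5. Precision of an added count.** With n = 60(1 - q)/2 non-ventilated subjects per arm, the 90% half-width is 1.645 x sqrt(p1(1 - p1)/n + p2(1 - p2)/n):

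- n = 27, 10% in both arms: 1.645 x sqrt(0.18/27) = 0.134
- n = 21, 20% vs 10%: 1.645 x sqrt(0.25/21) = 0.179
- n = 15, 30% vs 15%: 1.645 x sqrt(0.3375/15) = 0.247

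This approximation is rough at such counts. A Newcombe interval for 6/21 vs 3/21 uses 90% Wilson limits of 0.156-0.465 and 0.059-0.309. The difference is 0.143. The lower limit is 0.143 - sqrt(0.130^2 + 0.166^2) = -0.068, and the upper limit is 0.143 + sqrt(0.179^2 + 0.084^2) = 0.341. That is 14 points, 90% CI -7 to 34.

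**The case against.** **The restriction is a sensible analysis, plainly written.** Protocol 12.3.2 gives as examples "time to hospital discharge and time to mechanical ventilation discontinuation"; the second needs subjects who are on a ventilator. Protocol 12 leaves full detail to the SAP, and SAP 1 says that the SAP supersedes the protocol's analysis plan. This stands as a defence of the analysis. It does not confine the endpoint to those ventilated at baseline, and a general supersession clause does not identify a change that SAP 14.1 says does not exist.

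**The information is recoverable.** A reader might infer that progression to ventilation is invisible, or that nothing covers the excluded subjects. The documents do not support either reading. Their ventilation days enter total oxygen-therapy duration, itself a secondary endpoint. Baseline ventilation is tabulated by arm (SAP 5 and 5.2), so subtracting it from the concomitant-procedure count approximates the number newly ventilated, and the listings allow a direct count. This stands, with limits: SAP 5.5 names no analysis set, invasive and noninvasive support may be separate rows, and subjects ventilated earlier but off at baseline need separating. The result is a reconstruction, not a reported outcome.

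**The count is an addition.** No readable objective promises incidence of progression, and the study is primarily about safety, with no efficacy sizing. That is why the count should be descriptive only.

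**Imputation order.** A reader might infer that never-ventilated subjects who die receive the longest ventilation duration and distort the test. Exclusion first is the natural reading, so only an explicit sentence is needed.

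**Conclusion.** The point holds as a gap in definitions and an undeclared change. The secondary ventilation endpoint is narrowed to subjects ventilated at baseline, SAP 14.1 says nothing changed, and a first ventilation by escalation from oxygen is in neither readable ventilation endpoint. The number can be approximated from other outputs, but no specified unredacted output gives it directly by arm.

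This follows from the text and needs no assumption. Its size does: for 10-50% ventilated at baseline and 10-30% of the rest ventilated later, 30-54 of 60 subjects are excluded and about 3-16 first episodes are in neither endpoint. The primary safety endpoint is unaffected, and no claim is made about error rates. It is worth fixing because a named secondary objective is affected and the remedy is cheap.

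**What to change.** 1. **SAP 6.3.3.** For subjects not ventilated at baseline, add the number and percentage with first mechanical ventilation, and with ventilation or death, through one common stated day. For Part 2, report these by arm with the difference and its 90% CI. Label the result descriptive and show it separately from re-initiation. A common day is needed because follow-up ends 30 days after the last dose and so varies between subjects. Day 28 would be possible: a subject dosed only on Day 1 has planned follow-up to about Day 31 (1 + 30).
2. **SAP 6.2.1.** Label the duration analysis as restricted to subjects ventilated at baseline, and state that the exclusion is applied before the death or withdrawal imputation.
3. **SAP 14.1.** List the restriction as a change from the protocol.
4. **Before fixing the common day,** reconcile Protocol 9.5, which has procedures recorded as concomitant through the end-of-treatment visit, with Table 1 and its footnotes i and n, which extend recording to discharge and follow-up.

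The cost is SAP text and a little programming. Protocol 12 allows the SAP to add analyses, and Table 1 footnote i already has ventilatory support recorded with the time and date of changes. Whether any protocol clarification is needed depends on item 4. The downside is one more descriptive row with a wide interval, roughly +/-13 to +/-25 points in the settings shown, which must not be read as a test of efficacy.
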